# 9.4 Pharmacokinetic Analysis

# Pharmacokinetic Analysis

The DDI between APR-246 and pembrolizumab will be evaluated using popPK methods. The existing popPK model for APR-246 will be used to compare the observed plasma concentrations of APR-246 in presence of pembrolizumab with the predicted plasma concentrations assuming no DDI (visual predictive check). Additionally, the PK analysis dataset from this study will be integrated with the existing popPK dataset and the effect of pembrolizumab on APR-246 PK parameters will be tested as covariate in the model.

# Pharmacodynamic Analysis

The effect of APR-246-pembrolizumab combination therapy on soluble, tissue, genetic and/or imaging biomarkers will be summarized using descriptive statistics using the PK/pharmacodynamic analysis set. PK/pharmacodynamic relationships will be explored graphically and may be investigated by model-based analyses.

# **10.0 QUALITY CONTROL AND QUALITY ASSURANCE PROCEDURES**

### 10.1 Monitoring of the Study and Regulatory Compliance

The project manager, or designee, will make an initiation site visit to each institution to review the protocol and its requirements with the investigator(s), inspect the drug storage area, fully inform the investigator of his/her responsibilities and the procedures for assuring adequate and correct documentation. During the initiation site visit the eCRFs will be reviewed. Other pertinent study materials will also be reviewed with the investigator's research staff. During the course of the study, the monitor will make regular site visits in order to review protocol compliance, examine eCRFs and individual subject's medical records and assure that the study is being conducted according to pertinent regulatory requirements. All eCRF entries will be verified with source documentation. The review of medical records will be done in a manner to assure that subject confidentiality is maintained.

#### **10.2** Curricula Vitae and Financial Disclosure of Investigators

All Principal Investigators will be required to provide a current signed and dated curriculum vitae, a completed FDA Form 1572 and a financial disclosure statement to Sponsor's monitoring CRO. All Sub-Investigators will be required to provide a current curriculum vitae and a financial disclosure statement to Sponsor's monitoring CRO.

#### **10.3 Protocol Modifications**

No modification of the protocol should be implemented without the prior written approval of the Sponsor or the Sponsor's representative. Any such changes which may affect a subject's treatment or informed consent, especially those increasing potential risks, must receive prior approval by the IRB/IEC. The exception to this is where modifications are necessary to eliminate an immediate hazard to trial subjects, or when the change involves only logistical or administrative aspects of the trial (e.g., change in monitor, change in telephone number). Other administrative revisions which may impact the clinical portion of a study will be duly reported to the IRB/IEC by the Principal Investigator.

#### **10.4 Publication Policy**

The publication of the results of the study will be subject to the terms and conditions of the clinical trial agreement between the Sponsor and Investigators. Sponsor approval is required for publication of any data from this trial.

# **11.0 ETHICAL CONSIDERATIONS**

# **11.1 Informed Consent**

The investigator will obtain written informed consent from each subject, or their authorized representative, participating in the study. The form must be signed, witnessed and dated. The ICF will contain all the Essential Elements of Informed Consent set forth in 21 CFR, Part 50, the European Union Directive 2001/20/EC and its associated Detailed Guidances, European Union GCP Directive 2005/28/EC, the ICH Guideline for GCP, Section 4.8, and the terms of the Declaration of Helsinki (2013). Copies of the signed document should be given to the subject and filed in the investigator's study file, as well as the subject's medical record if in conformance with the institution's Standard Operating Procedures.

# **11.2 Institutional Review Board/Independent Ethics Committee**

The study will not be initiated without approval of the appropriate IRB/IEC and compliance with all administrative requirements of the governing body of the institution. This protocol, consent procedures, and any amendments must be approved by the IRB/IEC in compliance with current regulations of the FDA and the European Union as applicable and in accordance with ICH/GCPs. A letter of approval will be sent to the Sponsor prior to initiation of the study and when any subsequent modifications are made. The IRB/IEC will be kept informed by the investigator, Sponsor's monitoring CRO or the Sponsor, as required by national regulations, as to the progress of the study as well as to any serious and unexpected AEs.

# 11.3 Subject Privacy

In order to maintain subject confidentiality, all eCRFs, study reports and communications relating to the study will identify subjects by initials and assigned subject numbers; subjects should not be identified by name. In accordance with local, national or federal regulations, the investigator will allow the Sponsor or designee personnel access to all pertinent medical records in order to verify the data gathered on the eCRFs and to audit the data collection process. Regulatory agencies such as the U.S. FDA may also request access to all study records, including source documentation for inspection. Clinical information will not be released without the written permission of the subject as outlined in the subject consent form.

# 12.0 DATA HANDLING AND RECORD KEEPING

# 12.1 Data to be Entered Directly in the electronic Case Report Form

The eCRF will be the source record.

# 12.2 Recording of Data

Data collected during the study will be entered in the subject's eCRF by the investigational site staff. The staff will keep records of the subject's visit in the files considered as source documents for the site, e.g., hospital chart, research chart. The investigator will be responsible for the recording of all data on the eCRF and for submitting the data to the Sponsor or their designee in a timely manner. Should any value be significantly different from normal, the investigator will comment in the appropriate sections provided in the eCRF. The investigator will provide access to his/her original records to permit a representative from the Sponsor to verify the proper transcription of data.

# 12.3 Study Records

U.S. Federal laws require that an investigator maintain all study records for the indication under investigation for two years following the date a Product Licensing Application is approved or, if no application is to be filed or if the application is not approved for such indication, until two years after the investigation is discontinued and the FDA is notified.

# **APPENDIX I - Cockcroft-Gault Equation**

Males:			
Creatinine CL (mL/min)	=	Weight (kg) × (140 – Age) 72 × serum creatinine (mg	/dL)
Females:			
Creatinine CL (mL/min)	=	Weight (kg) × (140 – Age) 72 × serum creatinine (mg	× 0.85 /dL)

# **APPENDIX II - ECOG Performance Status**

Grade	
0	Fully active, able to carry on all pre-disease performance without restriction.
1	Restricted in physically strenuous activity but ambulatory and able to carry out work of a light or sedentary nature, e.g., light housework, office work.
2	Ambulatory and capable of all self-care but unable to carry out any work activities. Up and about more than 50% of waking hours.
3	Capable of only limited self-care, confined to bed or chair more than 50% of waking hours.
4	Completely disabled. Cannot carry on any self-care. Totally confined to bed or chair.
5	Dead.

# **APPENDIX III - Acceptable Contraceptive Methods**

- Male or female condom with or without spermicide
- Cervical cap, diaphragm or sponge with spermicide

# Highly Effective Contraceptive Methods That Are User Dependent a

*Failure rate of <1% per year when used consistently and correctly.* 

- Combined (estrogen- and progesterone-containing) hormonal contraception b

   Oral
  - Intravaginal
  - Transdermal
  - Injectable
- Progestogen-only hormonal contraception b
  - Oral
  - Injectable

# Highly Effective Methods That Have Low User Dependency

Failure rate of <1% per year when used consistently and correctly.

- Progesterone-only contraceptive implant b, c
- Intrauterine hormone-releasing system (IUS) b
- Intrauterine device (IUD)
- Bilateral tubal occlusion

# • Vasectomized partner

A vasectomized partner is a highly effective contraception method provided that the partner is the sole male sexual partner of the female of childbearing potential and the absence of sperm has been confirmed. If not, an additional highly effective method of contraception should be used.

# APPENDIX IV - New York Heart Association (NYHA) Classification

\*MET (metabolic equivalent) is defined as the resting VO2 for a 40-year-old 70kg man. 1 MET =  $3.5 \text{ mL O}_2/\text{min/kg}$  body weight.

# **APPENDIX V - Tumor Measurement Based on RECIST 1.1**

See the international criteria proposed by the RECIST Committee, version 1.1 for additional details on RECIST1.1.

Measurable disease will be defined as the presence of at least one measurable lesion that can be accurately measured in at least one dimension with the LD a minimum size of:

- > 10mm by CT scan (CT scan slice thickness no greater than 5 mm)
- 10mm caliper measurement by clinical exam (lesions which cannot be accurately measured with calipers should be recorded as non-measurable).
- 20 mm by chest x-ray.

For malignant lymph nodes to be considered pathologically enlarged and measurable, a lymph node must be  $\geq$  15mm in short axis when assessed by CT scan (CT scan slice thickness recommended to be no greater than 5mm). At baseline and in follow-up, only the short axis will be measured and followed.

All other lesions, including small lesions (LD < 10 mm or pathological lymph nodes with  $\geq$  10 to < 15 mm short axis) as well as truly non-measurable lesions, will be considered non-measurable. Lesions considered truly non-measurable include: leptomeningeal disease; ascites; pleural/pericardial effusion; inflammatory breast disease; lymphangitic involvement of skin or lung, abdominal masses/abdominal organomegaly identified by physical exam that is not measurable by reproducible imaging techniques.

All measurements should be recorded in metric notation, using calipers if clinically assessed. All baseline evaluations should be performed as close as possible to the treatment start and never more than 4 weeks before the beginning of the treatment. The same method of assessment and the same technique should be used to characterize each identified and reported lesion at baseline and during follow-up. Imaging based evaluation should always be done rather than clinical examination unless the lesion(s) being followed cannot be imaged but are assessable by clinical exam. Clinical lesions will only be considered measurable when they are superficial and  $\geq 10$  mm diameter as assessed using calipers (e.g. skin nodules). For the case of skin lesions, documentation by color photography including a ruler to estimate the size of the lesions is recommended.

Baseline Documentation of Target and Non-Target Lesions

All measurable lesions up to a maximum of 5 lesions total (and a maximum of two lesions per organ) representative of all involved organs should be identified as target lesions and will be recorded and measured at baseline.

Target lesions should be selected on the basis of their size (lesions with the longer diameter), be representative of all involved organs, but in addition should be those that lend themselves to reproducible repeated measurements.

A sum of the diameters (longest for non-nodal lesions, short axis for nodal lesions) for all target lesions will be calculated and reported as the baseline sum diameters. If lymph nodes are to be included in the sum, only the short axis is added into the sum. The baseline sum diameters will be used as reference to further characterize the objective tumor response of the measurable dimension of the disease.

All other lesions (or sites of disease) including pathological lymph nodes should be identified as non-target lesions and should also be recorded at baseline. Measurements are not required, and these lesions should be followed as "present" or "absent", or in rare cases "unequivocal progression".

# Evaluation of Target Lesions using RECIST 1.1 Criteria

NOTE: In addition to the information below, also see section 4.3.2 in the international criteria proposed by the RECIST Committee, version 1.1 for special notes on the assessment of target lesions.

Complete response (CR) – Disappearance of all target lesions. Any pathological lymph node (LN) (whether target or non-target) must have decreased in short axis to < 10 mm.

Partial response (PR) – At least a 30% decrease in the sum of the LD of the target lesions taking as reference the baseline sum LD.

Progressive Disease (PD) – At least a 20% increase in the sum of the LD of the target lesions taking as reference the smallest sum LD recorded since the treatment started including baseline if that is the smallest on study. In addition to the relative increase of 20%, the sum must also demonstrate an absolute increase of at least 5mm. The appearance of one or more new lesions also constitutes PD.

Stable disease (SD) – Neither sufficient shrinkage to qualify for PR nor sufficient increase to qualify for PD taking as references the smallest sum LD since the treatment started.

#### Evaluation of Non-Target Lesions using RECIST 1.1 Criteria

Complete response (CR) – Disappearance of all non-target lesions and normalization of tumor marker levels. All LN must be non-pathological in size (< 10 mm short axis).

Non-complete response (non-CR)/non-progression (non-PD) – Persistence of one or more non-target lesion(s) or/and maintenance of tumor marker level above the normal limits.

Progressive disease (PD) – Appearance of one or more new lesions and/or unequivocal progression of existing non-target lesions.

#### Evaluation of Best Overall Response using RECIST 1.1 Criteria

The best overall response is the best response recorded from the start of the study treatment until the end of treatment provided the confirmation criteria are met. To be assigned a status of PR or CR, changes in tumor measurements must be confirmed by repeat studies that should be performed > 4 weeks after the criteria for response are first met. If a CR/PR cannot be confirmed the original "response" should be considered stable disease. The best overall response will be defined according to the following table:

Overall Response First Time	Overall Response Subseque nt Time	BEST Overall Response
Point	Point	
CR	CR	CR
CR	PR	SD, PD, or PR 
CR	SD	SD provided minimum criteria for SD duration met, otherwise, PD
CR	PD	SD provided minimum criteria for SD duration met, otherwise, PD
CR	NE 	SD provided minimum criteria for SD duration met, otherwise, NE 
PR	CR	PR
PR	PR	PR
PR	SD	SD
PR	PD	SD provided minimum criteria for SD duration met, otherwise, PD
PR	NE 	SD provided minimum criteria for SD duration met, otherwise, NE 
NE	NE 	NE 

 If a CR is truly met at first time point, then any disease seen at a subsequent time point, even disease meeting PR criteria relative to baseline, makes the disease PD at that point (since disease must have

reappeared after CR). Best response would depend on whether minimum duration for SD was met. However, sometimes 'CR' may be claimed when subsequent scans suggest small lesions were likely still present and in fact the subject had PR, not CR at the first time point. Under these circumstances, the original CR should be changed to PR and the best response is PR.

 NE=inevaluable

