# 4.4 Duration of Therapy

Subjects may remain on study treatment to the end of the trial while deriving clinical benefit, unless unacceptable toxicity, progression, death or subject withdrawal. Subjects may remain on protocol therapy after disease progression if they are continuing to derive clinical benefit in the opinion of the investigator.

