#### 5.4.1 Study Treatment Discontinuation

Study treatment must be discontinued if:

- There is evidence of disease progression. Subjects who have PD but who are continuing to derive clinical benefit in the opinion of the investigator may continue to receive study treatment.
- A subject becomes pregnant.
- A subject is significantly non-compliant with the requirements of the protocol.
- A subject has an adverse experience that would, in the investigator's judgment, make continued participation in the study an unacceptable risk.
- The subject starts new treatment for their underlying disease.

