The same method of assessment must be used at all time points as was used at screening. Throughout the study it is critical that the same imaging methodology be applied, and contrast be consistently provided unless IV contrast becomes medically contraindicated during the course of treatment or the dose of contrast needs to be adjusted based on the subject's health status. In order for SD to be considered the BOR, it must occur  $\geq$  5 weeks following the first dose of study drug.

The first radiological assessment of tumor response status will be performed at Week 9 (±3 days), unless there is clinical indication warranting earlier radiologic imaging. If imaging at Week 9 shows SD, treatment will be continued and tumor assessments will be conducted at the next regularly scheduled imaging time point, i.e., every 6 weeks through the first year, then every 9 weeks, thereafter. Responses (PR or CR) should be confirmed no less than 4 weeks after the initial response, but generally at the next scheduled tumor assessment time point.

If the time point tumor assessment is PD, treatment may be continued and tumor assessments be repeated at least 4 weeks later, but generally at the next scheduled tumor assessment time point in order to confirm PD. If repeat imaging shows a reduction in the tumor burden compared to the initial tumor assessment demonstrating PD, treatment may be continued as per treatment schedule. If repeat imaging confirms PD, subjects will be considered for discontinuation from study treatment. In determining the tumor time point response, investigators should consider all target lesions as well as non-target lesions and new lesions. The decision to continue study treatment after the first evidence of PD is at the investigator's discretion based on the clinical status of the subject. However, subjects may continue to receive study treatment in the setting of PD if they are deriving clinical benefit in the opinion of the investigator.

Subjects may continue receiving study treatment while waiting for confirmation of PD if they are clinically stable as defined by the following criteria:

- Absence of signs and symptoms (including worsening of laboratory values) indicating disease progression
- No decline in ECOG performance status
- Absence of rapid progression of disease
- Absence of progressive tumor at critical anatomical sites (e.g., cord compression) requiring urgent alternative medical intervention

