If PD is confirmed and the subject is experiencing clinical benefit, the site may continue study treatment.

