# 8.2.1 Objective Response Rate

ORR is defined as the proportion of subjects who have BOR of CR or PR as measured by RECIST 1.1 (see APPENDIX V).

ORR is measured from the start date of the treatment period until date of death from any cause. Subjects who are lost to follow-up and the subjects who are alive at the date of data cutoff will be censored at the date the subject was last known alive.

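### Best overall response has no cut-off at progression, so a confirmed response first seen after PD can enter ORR and CBR, and for some subjects DCR

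*Combined protocol and SAP*

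**What the plan says.** **The response window.** Appendix V (Evaluation of Best Overall Response) states: "The best overall response is the best response recorded from the start of the study treatment until the end of treatment". The only condition attached is confirmation: "To be assigned a status of PR or CR, changes in tumor measurements must be confirmed by repeat studies", more than 4 weeks after the criteria are first met. Section 8.2.1 builds the rate on this: "ORR is defined as the proportion of subjects who have BOR of CR or PR as measured by RECIST 1.1". The same section, and the first secondary endpoint in the synopsis, then run ORR to death from any cause. DCR (8.2.2), durable SD rate (8.2.4) and CBR (8.2.5) are also defined through BOR.

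**Treatment after progression.** Section 4.4: "Subjects may remain on protocol therapy after disease progression if they are continuing to derive clinical benefit in the opinion of the investigator". Section 5.4.1, repeated in the synopsis: "Subjects who have PD but who are continuing to derive clinical benefit in the opinion of the investigator may continue to receive study treatment". Section 8.2 describes the case at issue: "If repeat imaging shows a reduction in the tumor burden compared to the initial tumor assessment demonstrating PD, treatment may be continued". It also covers progression that has been confirmed: "If PD is confirmed and the subject is experiencing clinical benefit, the site may continue study treatment".

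**The reference for PR.** Appendix V defines PR as: "At least a 30% decrease in the sum of the LD of the target lesions taking as reference the baseline sum LD". PD is measured from the smallest sum on study and is declared at one assessment.

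**PFS.** Section 8.3 and the synopsis count the first documentation of confirmed progression, or death.

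**The concern.** The endpoints are to be reported by RECIST 1.1, but neither response window ends at progression, and end of treatment is not progression in this trial. A tumour that progresses and later shrinks to 30% below its baseline sum meets every condition that the protocol sets for BOR = PR.

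The number of such subjects depends partly on whom the investigator keeps on treatment after PD, in an open-label trial whose scans are read by the investigator. Each expansion cohort may hold as few as 20 evaluable subjects, so one or two of them change the reported ORR visibly. Aligning Section 8.2.1 with Appendix V would remove the conflict between the two windows and leave this problem in place.

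**Working it through.** **1. The plan's own figures.** Table 7 gives two-sided 95% intervals for ORR. Section 9.3 names the method, Clopper-Pearson. With x responders in n subjects, the lower limit is the 2.5% quantile of Beta(x, n - x + 1) and the upper limit is the 97.5% quantile of Beta(x + 1, n - x). For 4/20 this gives 5.73% to 43.66% (Table 7: 5.7, 43.7). For 6/20 it gives 11.89% to 54.28% (Table 7: 11.9, 54.3). All six intervals in Table 7 reproduce.

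**2. Can a response after PD meet the stated conditions?** Let B be the baseline sum, and suppose that it is the smallest sum so far. Section 8.2 puts the first scan at Week 9 and later scans every 6 weeks through the first year.

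- Week 9: sum of at least 1.20 B, with an increase of at least 5 mm. This is PD.
- Treatment continues (4.4, 5.4.1, 8.2).
- Week 15 (9 + 6): sum of at most 0.70 B. This meets PR, because the reference is baseline.
- Week 21 (15 + 6): still PR. The gap of 6 weeks exceeds the 4 weeks required for confirmation.

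All scans fall between start and end of treatment, so under the Appendix V sentence BOR is PR. A new lesion that resolves follows the same path. A new lesion that persists does not, because later time points remain PD.

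**3. Which rates change, compared with closing BOR at PD?**

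- ORR: the subject is added.
- CBR: the subject is added, unless durable SD before PD already counted.
- DCR: the subject is added only without qualifying SD before PD. SD counts from 5 weeks and the first scheduled scan is at Week 9, so these are mainly subjects whose first scan is PD.
- SD scored after PD has the same opening: it could enter DCR, CBR or durable SD rate.

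ORR, DCR and CBR can therefore only rise. Durable SD rate can gain subjects in this way. It can also lose one, if a subject with durable SD progresses and then responds, because BOR is then no longer SD.

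**4. Size per subject.** One responder adds 1/n. The starting point is 20%, the lower end of the range expected in Section 9.1.

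| Cohort | No post-PD responder | One | Two |
|---|---|---|---|
| n = 20 | 4/20 = 20.0% (5.7-43.7) | 5/20 = 25.0% (8.7-49.1) | 6/20 = 30.0% (11.9-54.3) |
| n = 30 | 6/30 = 20.0% (7.7-38.6) | 7/30 = 23.3% (9.9-42.3) | 8/30 = 26.7% (12.3-45.9) |
| n = 40 | 8/40 = 20.0% (9.1-35.6) | 9/40 = 22.5% (10.8-38.5) | 10/40 = 25.0% (12.7-41.2) |

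At n = 20, two subjects span the whole expected range of 20% to 30%.

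**5. Frequency, by assumption only.** The documents give no rate of response after PD. If a proportion p of all subjects responds only after PD, the chance of at least one in 20 is 1 - (1 - p)^20: 33% for p = 0.02, 64% for p = 0.05 and 81% for p = 0.08.

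**6. PFS beside ORR.** If the repeat scan shows shrinkage, PD is not confirmed and there is no PFS event before the response. If PD is confirmed, treatment continues and a response follows, the PFS event is dated before the response begins. Section 8.2.3 defines DOR only as the duration of CR or PR and does not address this order of events.

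**The case against.** **No sentence tells the analyst to count these responses.** This is correct: the reading follows from the wording of the window plus treatment beyond PD. ORR is stated to be by RECIST 1.1, and Appendix V sends the reader to the published criteria for further detail. That source is not available here and cannot settle the point either way. The protocol does, however, write its own window sentence, and nothing in its text closes that window at PD.

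**The BOR table.** A reader might infer from the lack of a row starting with PD that the table permits a later response. It does not show that. There is no row starting with SD either; the table deals with confirming CR and PR. Where PD follows an unconfirmed CR or PR, its rows assign SD or PD and make no provision for a later upgrade. The table neither excludes nor licenses the subject in step 2, which leaves the window sentence.

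**A general contradiction between PFS, DOR and ORR.** A reader might infer that every such subject has progression dated before response. The documents do not support that, because PFS requires confirmed progression. The conflict is limited to PD confirmed before the response.

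**The size.** A reader might also infer a raised chance of passing an efficacy threshold, such as 6/20. Section 9.1 rests on precision and sets no test or go/no-go count for ORR, so no decision rule is affected. ORR is a secondary endpoint, and the intervals with and without one extra responder overlap widely. This limits the consequences; the upward direction stands.

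**Conclusion.** The point holds. As written, Appendix V and Section 8.2.1 allow a confirmed response after target-lesion PD, or after a new lesion that resolves, to count in ORR and CBR. It also counts in DCR where no qualifying SD came before PD. SD scored after PD could enter DCR, CBR or durable SD rate.

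Against a window that closes at PD, the effect on ORR, DCR and CBR is upward only. For ORR it is 5 points per subject at n = 20, 3.3 at n = 30 and 2.5 at n = 40. This assumes that the BOR sentence is applied literally and that the response is confirmed on treatment. The frequency is unknown, and the proportions in step 5 of the working are illustrative.

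**What to change.** - In Appendix V, state that BOR uses assessments from the start of treatment until first RECIST 1.1 progression or the start of new anticancer therapy, whichever comes first. In Section 8.2.1 and the first secondary endpoint of the synopsis, put the same window in place of the one that runs to death. Changing Appendix V alone would leave ORR running to death.
- Apply that window to ORR, DCR, durable SD rate and CBR.
- State how the progression date that closes BOR relates to the confirmed progression used for PFS. Otherwise a subject whose PD is not confirmed has BOR closed while PFS is still running.
- List responses seen after PD separately, as descriptive data outside ORR.

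The cost is a few sentences and one listing; treatment and imaging do not change. ORR may fall because post-PD responses drop out. It may also rise slightly relative to Appendix V: Sections 7.4 and 8.2 continue scans in subjects who stop treatment without progression, and those pre-progression scans would now count.
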